## 5.5 Safety Data

Clinical safety data includes serious adverse events (SAEs) and clinical laboratory markers both from the hospitalization and study intervention period and from the long-term follow-up period. Because these are critically ill newborns, we anticipate that most safety events will occur during the initial inpatient and treatment period. Safety event rates will be tabulated by study group and compared separately for each SAE using a multivariable logistic regression model, with adjustment for randomized treatment group, and randomization stratification factors of clinical recruitment site and HIE severity (moderate/severe). We will additionally create a per-patient aggregate count of SAEs and evaluate the rates between groups using a Poisson regression model with robust standard errors and adjustment for randomization stratification factors. For any safety events that occur infrequently (<2%), we will use Fisher's exact test to compare the rates between treatment groups. All safety events identified post-birth will be included in the primary analysis, while the secondary analyses will evaluate safety events occurring post-treatment with the first study drug dose as well as those events assessed as being possibly related to the study drug. Statistical significance is defined conservatively at the alpha=0.05 level with no correction for multiple outcomes.

## 5.6 Laboratory Data

Laboratory tests of organ injury are measured at baseline and at age 2-3 days as part of routine care. We will compare laboratory test data measured between study day 2 and 3 between treatment groups using analysis of covariance (ANCOVA) regression model, with adjustment for treatment group, the laboratory value measured at baseline, and the time between laboratory measurements. We will use a similar analytic approach to compare vital signs and growth parameters between treatment groups.

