Objectives	
1) To determine if 5 doses of Epo 1000 U/kg (birth weight) intravenous (IV) reduces the rate of death or neurodevelopmental impairment (mild, moderate, or severe) at 24 months of age.
 
2) To assess safety of Epo.
 
3) To determine whether Epo decreases the severity of HIE-induced brain injury as evidenced by early MRI and plasma biomarkers of brain injury.

Design	Prospective, randomized, double-masked, placebo-controlled study
Arms	
Treatment: Hypothermia (standard of care) plus Epo
 
Placebo: Hypothermia (standard of care) plus normal saline

Procedures	
 - Screen all cooled infants to evaluate eligibility for HEAL - Determine severity of encephalopathy using modified Sarnat exam - Consent and randomize patients - Randomized subjects receive five doses of either study drug or placebo - First dose administered within 24+2 hours of age (Study Day 1); subsequent doses given at the same time of day on Study Days 2, 3, 4, and 7 - Brain MRI and MR spectroscopy ideally performed between 96 and 144 hours post-birth, as part of routine clinical care - Blood collected prior to administration of first study drug dose, and on Study Days 2 and 4 (3 samples total, 1.5 mL each) - Urine (2 samples) collected on Study Days 0-1, and after completion of rewarming on Study Days 3-4 - Phone follow-up at 4, 8, 12, 18, and 24 months: parental questionnaires regarding intervening medical and developmental history, and developmental milestones (Warner Initial Developmental Evaluation of Adaptive and Functional Skills (WIDEA), 12, 18, and 24 months only); All phone interviews may be done in person if desired - 24-month in-clinic evaluation includes a standardized neurologic exam, Bayley III, Gross Motor Function Classification System (GMFCS) evaluation, Child Behavior Checklist (CBCL), and growth parameters. For extenuating circumstances, for example, COVID-19 restrictions, the in-person elements of the final endpoint evaluation may be performed up to 36 months of age. - Extended contact phone calls every 6 months from 2.5 through 8 years of age (WIDEA at 30 and 36 months)
Sites	At least 15, and up to 30 centers in the United States

TABLE OF CONTENTS

SYNOPSIS.....	8
1 STUDY OBJECTIVES	9
1.1 SPECIFIC AIMS.....	9
1.1.1 Aim 1: Efficacy	9
1.1.2 Aim 2: Safety	9
1.1.3 AIM 3: Biomarkers of Neonatal Brain Injury	10
1.2 ENDPOINTS.....	10
1.3 OVERVIEW OF STUDY DESIGN	10

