### 1.2 Design

This study is a randomized parallel group double-masked, placebo-controlled trial in neonates with HIE. We will enroll 500/2 = 250 subjects in each of two treatment groups: Epo-treated vs. placebo control. Eligible neonates will be enrolled and treated with either Epo or normal saline (on study day 1,2,3,4, and 7) and followed for a fixed period of 24 months ( $\pm 56$  days) for survival and neurological outcomes. For extenuating circumstances, for example, COVID-19 restrictions, the in-person elements of the final endpoint evaluation may be performed up to 36 months of age. The follow-up period was chosen to provide meaningful motor and cognitive outcomes, since CP and motor and cognitive deficits are more reliably diagnosed at 2 years of age. Enrolled children will be randomized, stratified by study site and severity of HIE, with equal likelihood to receive Epo or saline.

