### 1.3 Randomization

Randomization sequences will be created centrally by the Data Coordinating Center (DCC). The DCC will provide each site pharmacy with a randomization look-up table that pairs each study ID with a treatment allocation. Randomization is stratified by site and HIE severity level (“moderate” vs. “severe” HIE) based on the modified Sarnat score. The site pharmacy will then draw up the assigned study drug dose into a syringe, based on the randomization list. The appearance of the syringes of Epo and placebo are identical, thus the bedside staff remain masked. Only the research pharmacist and DCC biostatistician will be un-masked to treatment assignment. All parents, study and clinical staff, as well as all Clinical Coordinating Center (CCC) members, will remain masked to treatment assignment throughout follow-up. To ensure balance within clinical centers, the randomization will be implemented using a randomly permuted blocks design to ensure approximate balanced assignments within site and HIE severity level. The sequence of assignments for each site and stratum will be prepared in advance by the DCC.

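### The laboratory ANCOVA leaves out recruitment site and HIE severity, the randomisation strata; its intervals are too wide only to the extent that these factors predict the laboratory value beyond baseline

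*SAP*

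**What the plan says.** SAP 5.6 and Protocol 9.3.4 specify the same ANCOVA for laboratory tests taken on study days 2 to 3, "with adjustment for treatment group, the laboratory value measured at baseline, and the time between laboratory measurements". Neither section names another covariate. For the remaining continuous safety measures they say only: "We will use a similar analytic approach to compare vital signs and growth parameters between treatment groups".

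On allocation, SAP 1.3 states: "Randomization is stratified by site and HIE severity level". It uses a "randomly permuted blocks design to ensure approximate balanced assignments within site and HIE severity level". SAP 1.2 describes assignment "with equal likelihood to receive Epo or saline".

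Site and HIE severity are accounted for in the primary test (SAP 5.1), the secondary-outcome models (5.2), the SAE logistic and Poisson models (5.5), the circulating-biomarker comparisons (5.7) and the imaging regression (5.8). SAP 5.8 explains that they are included because they stratify the randomisation. Protocol 9.3.1 has a general rule to adjust for both, but it covers secondary outcomes and so does not reach the laboratory safety data.

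**The concern.** Allocation balanced within strata removes most between-stratum variation from the treatment contrast. A model without the strata leaves that variation in its residual, so its standard error exceeds the true sampling variability of the estimate. The p-value is then too large and the interval too wide.

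The direction matters because these are safety comparisons: a conservative test leans towards missing a difference in organ-injury markers. SAP 5.5 sets the opposite tone for SAEs: "Statistical significance is defined conservatively at the alpha=0.05 level with no correction for multiple outcomes". It also classes laboratory markers as clinical safety data beside the SAEs, yet only the SAE regressions carry the stratification factors. No reason is given for the difference.

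**Working it through.** **Inputs from the documents.** 250 infants per arm (SAP 1.2: "We will enroll 500/2 = 250 subjects in each of two treatment groups"). Sites: "At least 15, and up to 30 centers in the United States" (Protocol synopsis table), with 17 in the original proposal (SAP 7.5). Strata are site by severity, allocation 1:1. Alpha is 0.05.

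**Assumptions, because the documents give no figure.** Let r² be the share of the ANCOVA residual variance (after baseline value and time) explained by site and severity; range 0 to 0.20. Also assumed: 10% missing at random, so 500 × 0.9 = 450 analysed; two-sided test; block size 4; 25% severe HIE; baseline correlation 0.5; strata effect split equally between site and severity.

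**Benchmark.** The plan states no power, SD or interval width for the laboratory model. The nearest figure is the 0.26 SD detectable difference for imaging in SAP 7.3. With 225 per arm, (1.960 + 0.842) × √(2/225) = 0.264 SD at 80% power, which agrees with it.

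**Formulas.**
- Width with adjustment ÷ width without = √(1 − r²) × ratio of t quantiles. With 17 sites the degrees of freedom are 450 − 4 = 446 without and 450 − 4 − 16 − 1 = 429 with adjustment; the quantile ratio is 1.0001.
- Actual type I error of the model as written = 2 × [1 − Φ(1.96/√(1 − r²))].

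These were checked by simulating the stratified permuted-block design with 17 sites, 3,000 trials per setting (Monte Carlo standard error at 0.05: √(0.05 × 0.95/3000) = 0.004). Widths are in residual-SD units.

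| r² | Width ratio, formula | Mean width as written | Mean width adjusted | As written ÷ adjusted | Type I as written: formula | Type I as written: simulated | Type I adjusted: simulated |
|---|---|---|---|---|---|---|---|
| 0 | 1.000 | 0.3712 | 0.3724 | 0.997 | 0.050 | 0.055 | 0.054 |
| 0.02 | 0.990 | 0.3712 | 0.3686 | 1.007 | 0.048 | 0.045 | 0.050 |
| 0.05 | 0.975 | 0.3715 | 0.3631 | 1.023 | 0.044 | 0.045 | 0.051 |
| 0.10 | 0.949 | 0.3718 | 0.3539 | 1.051 | 0.039 | 0.041 | 0.047 |
| 0.20 | 0.895 | 0.3716 | 0.3334 | 1.115 | 0.028 | 0.030 | 0.047 |

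So the intervals as written are about 2%, 5% and 11% wider at r² of 0.05, 0.10 and 0.20. With 30 sites (run at r² of 0 and 0.02 only), adjusted ÷ unadjusted width is 1.007 and 0.998. Adjustment therefore costs up to about 0.7% of width when the factors carry no information.

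**Bias.** The mean error of the treatment estimate is at most 0.003 SD under either model.

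**Where the loss sits.** At r² = 0.20 the estimate's actual standard deviation is 0.0840 without and 0.0833 with adjustment, almost the same. The unadjusted model reports a standard error of about 0.3716/(2 × 1.965) = 0.0945. The stratified design has already delivered the precision; the model as written does not report it.

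**In detectable-difference terms.** Multiplying 0.264 by √(1 − r²) gives 0.257, 0.250 and 0.236 SD at r² of 0.05, 0.10 and 0.20. This borrows the imaging benchmark and is illustrative only.

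**The case against.** The strongest reply is that the loss may be nil. The baseline laboratory value already absorbs part of any site or severity effect, and the time covariate absorbs part of any difference in sampling interval. This stands: r² is unknown and may be close to zero, where adjustment buys nothing.

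A reader might infer that differing assays and sampling times across sites make the loss material. The documents do not support that. They report no assay differences, and Protocol 6.3.4 describes recommended time windows that match existing institutional practice.

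A reader might also take the laboratory model as the only unadjusted comparison in the SAP. It is not. Fisher's exact test for infrequent SAEs (SAP 5.5) and at interim looks (SAP 9) carries no such adjustment, and none is stated for the bootstrapped median MRI difference (SAP 5.3). The inconsistency is with the other regressions whose covariates are listed.

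Nor can it be said that the vital-sign and growth models omit the factors. Their covariates are not listed, and an omission is only inferred from the reference back to the laboratory approach.

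Finally, site terms are not free of difficulty. There could be up to 29 of them. The schedule of evaluations in Protocol 6.1 has laboratory values recorded as each site's routine care produces them, and Protocol 6.3.4 makes some tests conditional on clinical indication. Some tests may therefore have few values per site, and the fix has to provide for that.

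**Conclusion.** The omission is real and identical in both documents, and it is at odds with the reason SAP 5.8 gives for adjusting. Its consequence is conditional: no bias and no inflation of type I error, but a conservative test and intervals that are too wide if the strata predict the laboratory value beyond baseline. The effect is essentially nil for a share of 0 to 2% and about 2%, 5% or 11% of width at 5%, 10% or 20%. Those shares are assumed, and the simulated sizes also rest on the design assumptions listed in the working.

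The stronger reading, that an organ-toxicity signal will be missed, goes beyond what the documents show. At a 10% share the illustrative detectable difference moves only from 0.264 to 0.250 SD. The point is minor, concerns supportive safety data and leaves the primary analysis untouched.

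**What to change.** In SAP 5.6 and Protocol 9.3.4, add HIE severity and recruitment site to the laboratory ANCOVA. State that small sites will be pooled, or site fitted as a random effect, where a test has few values per site. List the same covariates explicitly for the vital-sign and growth comparisons. If the factors are to stay out, give the reason.

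The cost is a sentence or two of text; both variables are already held because they were needed to randomise. The statistical downside is intervals less than 1% wider if the factors turn out not to be prognostic.

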## 5.7 Circulating Biomarkers

Inflammation is thought to play an important role in HIE and CP. Biomarkers of inflammation that we measure include: interleukin (IL)-1 $\beta$ , IL-6 and IL-8 and TNF- $\alpha$ . Putative biomarkers of brain injury in neonatal HIE include: glial fibrillary acidic protein (GFAP), ubiquitin C-terminal hydrolase-L1 (UCH-L1), S100B, Tau, and neuron-specific enolase (NSE). We will select a random subset of 200 subjects (100 treated and 100 controls with each group, for example, including both moderate and severe HIE) to measure circulating biomarkers of inflammation and brain injury. We will collect 3 plasma samples from each infant at the following time points based on hour of age: < 24 hours; Study Day 2; Study Day 4. Our analysis will focus on time-specific comparisons of the mean biomarker measure across treatment

groups using appropriate regression methods while controlling for site and HIE severity. In addition, we will conduct longitudinal analysis using linear mixed models that permit an omnibus test across all four measurement times and allow inference on differential rates of change across treatment groups.

## 5.8 Neuroimaging Outcomes

The primary neuroimaging outcome measures are: (1) the total injury score (derived from the HEAL/Wash U MRI scoring system above) and (2) the ratio of lactate/NAA determined for the left thalamus and parietal white matter from the quantitative MRS data. For the MRI injury score and the lactate/NAA ratio, we will use linear regression to compare Epo treated patients to controls while adjusting for site and HIE severity since these are factors used to stratify the randomization. If we have missing data due to either early patient death or other factors (e.g., family declines MRI or infant is unable to complete all the sequences), we will estimate the resultant sampling bias by comparing our final neuroimaging sample to the overall HEAL sample with regard to patient demographics and primary outcome data.

# 6. Compliance, Retention, and Missing Data

## 6.1 Adherence and Retention

Our major analyses are based on the modified ITT principle. We do not anticipate that non-adherence will be a major issue since the treatment is directly observed during a short in-hospital time frame. We will assess non-compliance, with particular focus on study treatment dosing and timing. If there are more than minimal issues, that will justify quantifying and characterizing non-adherence and doing a per-protocol analysis. In addition, site selection included having a committed neonatology follow-up program, and we expect >90% retention.

## 6.2 Missing Data and Dropouts

We will strive to sustain excellent participant involvement throughout the study and we have achieved 90%+ follow-up rates in numerous prior studies. The UW DCC will generate automated nightly reports, available to staff at the study sites, identifying these fields with a request to discuss and prevent further missingness. Important data elements will be prospectively monitored to examine patterns of missingness.

## 6.3 Handling

In final manuscripts and analyses, the number of non-responders will be enumerated by study arm according to CONSORT guidelines. We will conduct a missing data analysis to describe and characterize enrolled participants who do not provide further response due to attrition or dropout. We will also conduct sensitivity analyses using 10-fold multiple imputation to assess the robustness of the results when missing data are imputed.

## 6.4 Statistical Uncertainty

Given the type of missing data we expect in the proposed study, missing completely at random (MCAR) or missing at random (MAR), both methods we propose to utilize for missing data properly account for statistical uncertainty due to missingness and will provide accurate confidence interval coverage.

## 6.5 Sensitivity Analysis

We will assess the sensitivity of inferences made from missing data methods first by using the two previously described methods for dealing with missing data, and secondly by imputing missing data under both pessimistic and optimistic scenarios to provide bounds on the statistical uncertainty. The

characteristics of non-responders will be summarized in our final report where we will present the sensitivity of the treatment effect due to missing data.

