### **5. Data Analyses**

#### **5.1 Primary Outcome**

The primary analysis will be a test of equality of the rate of the primary outcome (death or neurodevelopmental impairment (NDI)) across the two randomized investigational groups. Specifically, we will use a likelihood ratio test based on logistic regression, with stratification by recruitment center and HIE severity. We will perform modified Intention to Treat (mITT) analysis and expect minimal non-compliance due to the nature of the intervention in relation to in-patient care. For the primary endpoint, we expect uniform and complete ascertainment of death but may not evaluate all subjects for developmental impairment. We plan to perform a primary analysis based on complete cases and will exclude those subjects for whom vital status is known (alive) but NDI cannot be assessed. Sensitivity analysis will use multiple imputation to evaluate the potential impact of any missing data. Secondary analysis will consider an ordered categorical two-year status measure (death/severe or moderate impairment/mild impairment/normal), and analysis will be based on generalized Wilcoxon tests.

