## 7. Sample Size and Accrual

### 7.1 Primary Outcome Sample Size Calculations

Our proposed HEAL sites report an overall mortality rate of 14%. Using three large sites that participated in the phase II study (UCSF, Wash U, CNMC) we can also estimate the rates of neurodevelopmental impairment: death = 14%; moderate-severe impairment = 18%; mild impairment = 17%; and normal = 51%. Therefore, we anticipate a control primary outcome rate of 49% (death or NDI).

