### 7.1.4 Power and Sample Size for Primary Outcome

In order to determine the necessary sample size for efficacy evaluation we need to formulate assumptions for the primary outcome rate in the Epo treated and control groups. The primary outcome measure is the composite rate of death or NDI, and current cohort studies suggest that the primary outcome occurs among 49% of infants treated with hypothermia alone (standard of care). Based on human data presented in Rogers et al. (2014), animal studies including Traudt et al., and the NEATO phase II data we assume that 33% of treated infants will die or have NDI, corresponding to a relative risk of 0.67. Assuming an intervention rate of 33% yields greater than 90% power, while we have 88% power for an alternative of 34% (**Table 4**). In order to compute power, we assume a 90% follow-up rate with n=225/250 subjects evaluated in each arm.

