## 7.2 Sample size for efficacy secondary outcomes

Our key secondary long-term outcome is an ordered categorical 24-month status measure that classifies subjects as: dead; moderate or severe impairment; mild impairment; and normal. Use of this measure allows a detailed assessment of potential shifts in the distribution of outcomes toward improved status associated with treatment. Statistical analysis of this outcome will use a generalization of the Wilcoxon test that controls for recruitment site and HIE severity. Regression models for ordered categorical outcomes can also be used to provide adjusted treatment effect estimates.

To consider power we have used 2013 data from three large sites participating in the phase II trial (UCSF, Wash U, CNMC) to estimate the distribution of outcomes within the control group. We calculate power for the stratified Wilcoxon test assuming a set of alternatives that are consistent with the assumption of a 33% rate of death or impairment (Scenarios 1 and 2, **Table 5**) or a 32% rate (Scenarios 3 and 4, **Table 5**) associated with intervention that was used to power the primary analysis. We assume a small effect on the death rate, and compute power for alternative shifts in the distribution of outcomes. For example, in Scenario 1 we assume no reduction in the death rate, and an 8% reduction in the moderate/severe category (relative risk = 0.55), and an 8% reduction in the rate of mild impairment (relative risk = 0.50) which yields 81% power using a two-sided alpha=0.05 test. Scenario 3 considers a larger reduction in the rate of moderate/severe and a smaller reduction in the mild category and yields 90% power. Scenarios 3 and 4 consider a 32% overall rate of impairment or death and yield 90% or greater power. Therefore, our study is adequately powered to detect modest but clinically important shifts in the outcome distribution.

**Table 5. Power analysis for a four-level outcome measure with n=500 patients randomized and assuming 10% loss to follow-up**

	Neurodevelopmental Impairment			Mortality	Power
	Normal	Mild	Moderate/Severe		
Placebo Arm	51%	17%	18%	14%	--
Epo Arm					
Scenario 1	67%	9%	10%	14%	81%
Scenario 2	67%	11%	10%	12%	86%
Scenario 3	68%	9%	9%	14%	86%
Scenario 4	68%	11%	9%	12%	92%

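### SAP 6.5 leaves its pessimistic and optimistic imputations undefined, and the reading chosen decides whether the primary result looks fragile; a tipping-point grid is needed

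*SAP*

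**What the plan says.** SAP 5.1 makes the primary analysis a complete-case comparison. Deaths are expected to be fully ascertained, so the excluded children are known survivors whose NDI could not be assessed. The test is specified as follows: "we will use a likelihood ratio test based on logistic regression, with stratification by recruitment center and HIE severity".

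The planned checks on missing data are:
- multiple imputation (SAP 5.1 and 6.3);
- inverse probability weighting, described in Protocol 9.3.6.1 but not in the SAP;
- "imputing missing data under both pessimistic and optimistic scenarios to provide bounds on the statistical uncertainty" (SAP 6.5, with the same wording in Protocol 9.3.6.1).

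SAP 6.4 justifies the methods on the expectation that data are missing completely at random or at random. The scenario imputation is therefore the only check that leaves that assumption. Neither document states the value imputed in each arm, whether the arms are moved in opposite directions, or how the bounds are to be read.

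On the amount of loss, SAP 7.1.4 says "we assume a 90% follow-up rate with n=225/250 subjects evaluated in each arm", while SAP 6.1 says "we expect >90% retention".

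**The concern.** At least two constructions fit the SAP wording. In one, the pessimistic case sets every missing Epo infant to impaired and every missing placebo infant to unimpaired, and the optimistic case does the reverse. In the other, all missing infants in both arms get the same value, first all impaired and then all unimpaired. Most positive trials would fail the first check at 10% loss, and almost none would fail the second. With no definition, the choice could be made after unblinding.

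Neither version answers the question a reader will ask: how different would the unassessed children have to be, between arms, before the conclusion changed?

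**Working it through.** **Inputs.** There are 250 infants per arm (SAP 1.2), with 225 evaluated and 25 missing per arm (SAP 7.1.4). The event rates are 49% for placebo (SAP 7.1) and 33% for Epo (SAP 7.1.4). I assume a two-sided alpha of 0.05; the SAP states this for the ordinal outcome ("yields 81% power using a two-sided alpha=0.05 test") but not beside Table 4. Strata are ignored.

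**The plan's own figure.** Power = Φ{[d − 1.96·√(2p̄(1−p̄)/n)] / √[(p1(1−p1)+p2(1−p2))/n]}, with n = 225 and d = 0.16. This gives 93.5%. With a continuity correction (d reduced by 1/n) it gives 92.1%, against 92% in Table 4. The corrected formula gives 95.0%, 88.2% and 83.2% for the 32%, 34% and 35% rows, which match the stated 95%, 88% and 83%.

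**Arm-opposed extremes, 25 missing per arm.**
- *Planned effect, pessimistic bound.* Expected placebo rate: 225×0.49/250 = 44.1%. Expected Epo rate: (225×0.33+25)/250 = 39.7%. The difference shrinks from 16 to 4.4 points. Significance needs about 1.96×√(0.419×0.581×2/250) = 8.65 points. The SD of the difference is √[225(0.2499+0.2211)]/250 = 4.12 points. So P(significant) ≈ Φ((4.4−8.65)/4.12) = 15%.
- *No effect (49% in both arms), optimistic bound.* The imputation adds 25/250 = 10 points in favour of Epo. The threshold is about 8.76 points and the SD 4.24, so P(significant for Epo) ≈ Φ(0.29) = 61%.

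Exact enumeration of the two binomials gives 15.4% and 62.9%, and the pooled z test and the unstratified likelihood ratio test agree. Hence 84.6% of all planned-effect trials are non-significant under the pessimistic bound. Among those significant on complete cases, 83.5% lose significance. Simulations with deaths fully ascertained and only survivors missing give 82-85% for the latter and 62-63% for the no-effect case.

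**By amount missing (arm-opposed).**

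| Missing per arm | No effect: optimistic bound significant for Epo | 49% vs 33%: significant results lost |
|---|---|---|
| 5 (2%) | 7% | 7% |
| 10 (4%) | 15% | 22% |
| 12 (4.8%) | 19% | 29% |
| 20 (8%) | 44% | 65% |
| 25 (10%) | 63% | 84% |

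**Same value in both arms, 25 missing per arm.** The planned difference becomes 225×0.16/250 = 14.4 points. Power is 92.0% with all missing impaired and about 92.5% with all unimpaired. Between 1.0% and 1.5% of significant results are lost. With no effect, about 2.1% of trials are significant in each direction.

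**What the corners hide.** Take a trial at the planned rates, 74/225 on Epo and 110/225 on placebo: z = 0.16/0.04635 = 3.45, p = 0.0006. The arm-opposed pessimistic bound is 99/250 against 110/250: z = 0.044/0.04412 = 1.00, p = 0.32, which looks fragile.

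The expected NDI rate among placebo survivors is (49−14)/86 = 41%, or about 10 of 25. With 10/25 missing placebo infants impaired, placebo has 120/250:
- 24/25 missing Epo infants impaired: 98/250, z = 0.088/0.04435 = 1.98, p = 0.047;
- 25/25 impaired: 99/250, z = 0.084/0.04438 = 1.89, p = 0.058.

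Significance goes only if every missing Epo infant is impaired. The rate planned among Epo survivors is (33−14)/86 = 22% with 14% mortality, or (33−12)/88 = 24% with 12%. The result is robust to any plausible departure, and the pessimistic corner alone does not show it.

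**The case against.** The strongest reply is that these are bounds with no decision rule attached. SAP 6.5 promises to present sensitivity and does not declare a result robust or not. Read as a pair, a no-effect trial with one bound favouring Epo will normally have the other on the opposite side, which is an honest display of uncertainty. That stands, and the 63% should not be read as a false-positive rate of the trial.

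A reader might also infer four stronger things that the documents and figures do not support.
- **That the bounds cannot separate robust from fragile results.** Under the arm-opposed reading, a no-effect trial is significant on both complete cases and the pessimistic bound with probability about 0.000005, against 15.4% at the planned effect. Passing is highly informative.
- **That the number missing alone fixes the outcome.** At 10% loss the share of significant results lost is 22% if the true Epo rate is 25%, 64% at 30% and 91% at 35%.
- **That the pessimistic bound reverses the finding.** It usually only removes significance. The estimate reaches zero or changes sign in 9.4% of significant trials, and 0.08% of planned-effect trials become significantly unfavourable to Epo.
- **That the plan expects to lose 25 infants per arm.** That is the power assumption, and retention above 90% is expected. Masked adjudication of partial data (SAP 2.4), GMFCS by phone (Protocol 6.3.8) and the extended visit window should also reduce loss.

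The two readings are not exhaustive either. A milder arm-opposed case, with missing Epo infants at 49% and missing placebo infants at 33%, leaves 85% of planned-effect trials significant. That supports the point: everything between the corners is unspecified.

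**Conclusion.** The concern holds in a limited form. The only check outside missing at random is undefined, and the plausible readings give opposite impressions: at 25 missing per arm, 83.5% of significant results are lost under arm-opposed extremes and 1.0-1.5% under a common value. If arm-opposed extremes are meant, failing the pessimistic bound at about 10% loss says little about robustness, although passing it says a great deal. The problem shrinks with better follow-up, to about 29% lost at 12 missing per arm.

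The figures rest on equal loss in both arms, every missing child being imputed to the extreme, an unstratified test at two-sided 0.05, and the plan's own rates. The complete-case primary analysis and its power are not in question. The gap lies in what can be concluded about robustness afterwards, and it is worth closing before unblinding.

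**What to change.** In SAP 6.5, with a matching change in Protocol 9.3.6.1:
1. State the extreme scenarios by arm, including the value given to missing infants in each.
2. Keep those extremes as the corners of a prespecified two-way tipping-point grid. Impute NDI among known survivors with missing NDI over arm-specific rates from 0 to 100%, or use delta-adjusted multiple imputation on the logit scale with a separate shift for each arm.
3. Refit the primary model, with its site and HIE severity strata, at each grid point. Report the treatment estimate, its confidence interval and the boundary where p crosses 0.05.
4. Judge that boundary against the observed NDI rates among assessed survivors in each arm.

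The cost is SAP wording and a little programming on top of the multiple imputation already planned. No new data are needed, the primary analysis is unchanged, and the existing bounds are kept.
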